4. STUDY DESIGN AND INVESTIGATIONAL PLAN

4.1 Design: Phase I/II single-arm dose-escalation non-masked interventional study

The study will be a phase I/II, non-masked (not blinded), interventional study aimed at treating up to 16 HLA*A0201 patients with metastatic MCC that has progressed despite immune checkpoint inhibitor therapy (PD-1 or PD-L1 inhibitor). All patients will receive study interventions.

[figure not shown]
Patients may receive the other, standard-of-care portions of the ATTAC regimen in addition to T cells. This includes the PD-L1 inhibitor avelumab. Please see **Section 6/treatment plan** for further details).

Patients will receive up to two T cell infusions. Please see **6.4.4** for details regarding selection of one versus two cycles of T cell therapy.

Any patient experiencing treatment related grade 3 or 4 toxicity (except for the expected toxicity specifically excepted/outlined in **Section 12.6**) will immediately stop receiving T cell infusions, avelumab, and class I HLA upregulation. They will receive treatment as appropriate for their condition (see **Section 7** and **Section 12**). They will continue to be followed for response/outcome. Patients with infusion reactions to avelumab may receive pembrolizumab for first or subsequent infusions.

As a criterion for enrollment into the trial, participants must agree to biopsies of tumor tissue if medically feasible. A minimum of 4 biopsies will be performed as clinical status allows: prior to interferon gamma administration, 1-2 days prior to T cell infusion, 2 weeks after, and 12 weeks after the first full dose T cell infusions. However, should there be no tumor tissue that is accessible for biopsy, patients will still be considered for participation at discretion of the investigator. Similarly, should an investigator or treating physician determine that a biopsy cannot be performed safely for clinical reasons (e.g., no safe approach), biopsies may be cancelled or retimed at the investigator or treating physician's discretion.

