6.5.2 Avelumab or pembrolizumab infusion

Avelumab will be administered as standard of care. Currently, the FDA recommended dosing is 10 mg/kg over the duration of 1 hour (-10/+70 minutes) at an interval of once every 2 weeks.

Premedications suggested by package label include pretreatment with H1 blockers (diphenhydramine 12.5mg to 50 mg PO or IV, or equivalent) and acetaminophen PO 500 to 650 mg for first several doses.

First avelumab dose is intended 14 +/- 3 days after first T cell infusion up to 50 weeks (total of 25 infusions) or longer, as clinically indicated under the standard of care or until Off Study Criteria are met as described in **Section 10**. The first dose of avelumab will be calculated based on the actual weight of the participant determined at study entry. As avelumab is being administered as standard of care, if alternate doses or schedules are approved by the FDA for avelumab for treatment of advanced MCC (for instance q4 week dosing or flat instead of weight-based dosing), these doses and schedules may be substituted at the discretion of the investigator and treating oncologist. Following first avelumab infusion, participants will be observed for 1 hour post infusion for potential infusion-related reactions. Participants will receive avelumab once every 2 weeks for 50 weeks or until the criteria in **Section 11.7** (Off Study Criteria) are met. Modifications of the infusion rate due to infusion-related reactions and management of acute infusion reactions are below as recommended in product label.

The first avelumab infusion after each T cell infusion should be administered at Fred Hutch for monitoring in case of acute adverse event. Subsequent infusions may be given locally by a licensed oncology professional experienced in prescribing immunotherapy. A “Dear Physician” letter detailing the study treatment and providing contact information to the study team including emergency contact information will be provided to local/non-Fred Hutch oncologists.

Monitoring exams and blood work associated with avelumab infusion will be performed clinically at the discretion of the treating oncologist and in keeping with institutional standards for avelumab infusion.

If pembrolizumab is given instead of avelumab, it will be administered over 30 minutes intravenously with similar monitoring as above and without premedications unless at the direction of the clinical team.

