11.1 Visits required to be at Fred Hutch/UWMC

Many of the patients with MCC travel >500 miles to receive care at Fred Hutch/UWMC. Although up to two T cell infusions are given, the avelumab is given every 2 weeks for a year (or pembrolizumab every 3 weeks for a year), as a standard of care treatment, using standard of care FDA approved dosing and frequency. Therefore, for interventions surrounding T cell infusions and the first avelumab or pembrolizumab infusion after each T cell infusion, we request care to be at Fred Hutch/UWMC, in order to ensure safety. However, for "maintenance" avelumab or pembrolizumab visits, we will allow patients to receive these infusions with their local/primary oncologist if that is patient preference, except as detailed below.

Leukapheresis, pre-treatment biopsy, and pre-treatment physical exam, and treatment consenting need be performed through Fred Hutch/UWMC.

For cycle 1 of T cell therapy, the patient is required to receive care at Fred Hutch/UWMC and stay within 30 minutes of Fred Hutch/UWMC from the first dose of interferon gamma (day -5) through T cell infusion and the 28-day dose-limiting toxicity (DLT) period thereafter. This period includes the first (d+14) avelumab or pembrolizumab infusion, if eligible/stable. If the patient shows no signs of T cell mediated toxicity within 17 days of T cell infusion (and 3 days for PD-1/PD-L1 inhibitor infusion), they may return to the care of their treating oncologist with permission of the PI.

Day 28, 42, 56, 70, and 84 avelumab (or day 35, 56 and 77 pembrolizumab) may be given locally or at Fred Hutch and research blood may be shipped/mailed. Day +84/cycle 1 evaluations including research and clinical blood work, exams, imaging, and biopsy should be performed if possible at Fred Hutch or UWMC. Patient must remain within 30 minutes of Fred Hutch/UWMC for second T cell infusion and at least 28 days thereafter, during which avelumab or pembrolizumab is likely to be administered.

Subsequent avelumab or pembrolizumab may be given locally. If the patient shows no signs of T cell mediated toxicity within 17 days of T cell infusion (and 3 days for PD-1/PD-L1 inhibitor infusion), they may return to the care of their treating oncologist with permission of the PI.

6 month, 9 month and 12 month imaging and laboratory evaluations are requested to be performed at Fred Hutch; however, they may be performed locally if circumstances preclude travel to Fred Hutch.

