13. STATISTICAL CONSIDERATIONS

13.1 Sample size and Power

Our study is a phase I/II, non-blinded interventional trial. Our target sample size is up to 16 patients (8 per year/2 years). This target is chosen for three reasons: it is achievable from an enrollment standpoint (our clinic sees between 15-20 potentially eligible patients per year), it is logistically possible from a funding and cell processing facility standpoint, and it allows >80% power to observe a statistically significant (at one-sided 0.05 level) efficacy signal that is clinically meaningful. (see below for details). With the eligibility expansion, we expect roughly 12 patients will receive a PD1 checkpoint inhibitor. For some analyses, all 16 patients will be analyzed, yet some analyses will be restricted to patients who receive a PD1 checkpoint inhibitor. See below for the impact of this on statistical power.

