The above toxicity considerations above will be examined among all patients, regardless of their PD1-contraindication status and whether they get PD-1/PD-L1 inhibition therapy on the trial. The delay of PD-1/PD-L1 inhibition until 14 days after T cell infusion will help differentiate toxicity related specifically to PD-1 axis inhibition. However, if any patient who does not receive a checkpoint inhibitor develops a toxicity, enrollment to such patients will be suspended pending review by the DSMB and the PI, at which point a decision will be made to continue the trial as is, modify the trial, and halt enrollment of patients for whom a checkpoint inhibitor is contraindicated.

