13.3.2 Definition of success and power of success

Responses to alternative therapies in this population of patients with advanced MCC resistant to PD1-axis blockade are rare, and we therefore will use a 5% response rate as the fixed benchmark upon which we hope to improve with the proposed treatment. If the true response rate with TCR-transduced cells is 25%, 16 patients yield 84% power to detect a statistically significantly improved response rate (one-sided .05) over the fixed rate of 5%. Three or more responses among 16 pts would occur with probability .04 if the true response rate is 5%, so if three or more patients respond (an observed response rate of at least 19%), we will conclude that this regimen is potentially efficacious and worthy of further

study. If power is instead assessed among the anticipated 12 patients who will receive a checkpoint inhibitor, the statistical power is reduced to 78%.

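### The checkpoint-inhibitor subset and the special suspension rule are defined by receipt of a drug first given about day 14, not by contraindication at enrollment

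*Combined protocol and SAP*

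**What the plan says.** Section 13.1 expects roughly 12 of 16 patients to be given an inhibitor and states that "some analyses will be restricted to patients who receive a PD1 checkpoint inhibitor". Section 13.3.2 gives a separate power figure, 78%, for "the anticipated 12 patients who will receive a checkpoint inhibitor".

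The last paragraph of 13.2.2 examines toxicity in all patients, whatever their contraindication status and whether or not they are given an inhibitor. It then adds a special rule: "if any patient who does not receive a checkpoint inhibitor develops a toxicity, enrollment to such patients will be suspended pending review". The outcomes listed after review are to continue, to modify the trial, or to stop enrolling patients in whom an inhibitor is contraindicated.

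Three other places determine who receives the drug:

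- Section 6.5.2: "First avelumab dose is intended 14 +/- 3 days after first T cell infusion". Section 6.5.1 gives the same 14-day start for pembrolizumab.
- Section 11.1, on the 28-day toxicity period: "This period includes the first (d+14) avelumab or pembrolizumab infusion, if eligible/stable".
- Section 4.1: a patient with a related grade 3 or 4 toxicity, other than those excepted in 12.6, "will immediately stop receiving T cell infusions, avelumab, and class I HLA upregulation". Sections 11.7 and 13.2.2 contain similar stops.

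Contraindication, by contrast, is known at entry. Sections 5.3.1, 5.3.9 and 6.5 identify patients (autoimmune history, or a prior high-grade immune-related event on PD-1 axis blockade) who will not be given an inhibitor on trial.

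**The concern.** Two groups are being treated as one: patients who cannot have an inhibitor, fixed at baseline, and patients who did not get one, known only after about two weeks of follow-up. They differ by the patients who were meant to have an inhibitor but had a stopping toxicity, deteriorated or died first.

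This matters in two places. A response rate restricted to receivers is conditional on reaching the first dose, so early failures can drop out of its denominator. And the suspension rule, read as written, can be tripped by a patient with no contraindication, although the question put to the DSMB and the investigator is whether contraindicated patients should still be enrolled. Enrollment can be suspended only for a class recognizable at enrollment, so a trigger based on receipt does not match its own action.

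**Working it through.** **Reproducing the plan's figures.** Inputs from 13.3.2: "If the true response rate with TCR-transduced cells is 25%, 16 patients yield 84% power", null rate 5%, one-sided 0.05. The normal approximation with the null variance in the critical value is

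power = Φ{[0.20 − 1.645·√(0.05·0.95/n)] / √(0.25·0.75/n)}.

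- n = 12: (0.20 − 0.1035)/0.125 = 0.77, power 0.780 (plan: 78%).
- n = 16: (0.20 − 0.0896)/0.1083 = 1.02, power 0.846 (plan: 84%).
- Exact binomial: at least 3 of 16 has type I error 0.043 (plan: .04) and power 0.80. At least 3 of 12 has 0.020 and 0.61.

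The 13.2.2 boundary, computed exactly, gives suspension probabilities of 0.062 at 20% toxicity and 0.847 at 60% (plan: 0.06 and 0.84).

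**Who becomes a non-receiver.** The first dose is due around day 14. A non-excepted related grade 3-4 toxicity before then ends active treatment, including the inhibitor. Such a patient is a non-receiver with a toxicity, which is the literal trigger condition, whether or not any contraindication exists.

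**Suspension rule.** Assume 12 planned-inhibitor patients (13.1) and 16 − 12 = 4 contraindicated patients. Let q be the toxicity rate in both groups and f the share of toxicities before the first inhibitor dose. The documents use 20% (13.2.2) and 25% (synopsis) as planning scenarios for q. They give no value for f.

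- Trigger by contraindication: 1 − (1 − q)^4.
- Trigger by receipt: 1 − (1 − q)^4·(1 − qf)^12.

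At q = 25%, the first is 1 − 0.3164 = 0.68. With f = 50% the second is 1 − 0.3164·0.875^12 = 1 − 0.3164·0.2014 = 0.94. With a 5% pre-day-14 rate it is 1 − 0.3164·0.95^12 = 1 − 0.3164·0.5404 = 0.83.

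| q | Contraindicated only | Receipt, f = 25% | f = 50% | f = 75% |
|---|---|---|---|---|
| 20% | 0.59 | 0.78 | 0.88 | 0.94 |
| 25% | 0.68 | 0.85 | 0.94 | 0.97 |

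**Subset response rate.** Let e be the share of planned patients lost before the first dose as non-responders (assumed; not in the documents). The rate among receivers is p/(1 − e). For p = 25% and e = 10%, 0.25/0.90 = 27.8%. The last two columns apply at least 3 of 12 to 12 receivers at the inflated rates.

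| e | True 5% appears as | True 25% appears as | P(≥3/12), true 5% | P(≥3/12), true 25% |
|---|---|---|---|---|
| 0 | 5.0% | 25.0% | 0.020 | 0.61 |
| 10% | 5.6% | 27.8% | 0.026 | 0.69 |
| 20% | 6.3% | 31.3% | 0.035 | 0.78 |
| 30% | 7.1% | 35.7% | 0.049 | 0.86 |

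If instead 12 patients are planned and the subset shrinks as they are lost (critical value reset to the number left), the effect on the test is smaller: at e = 30% the two probabilities are 0.037 and 0.69.

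**The case against.** The strongest reply is that 13.2.2 plainly means contraindicated patients. Its closing clause says so, suspending enrollment makes sense only for a class known at entry, and 13.1 ties the figure of 12 to the eligibility expansion. That is probably the intent. But the same paragraph first distinguishes contraindication status from getting the inhibitor, so the two are not used as synonyms, and a suspension rule should not depend on readers overriding its wording.

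Several limits stand:

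- Grade 3-4 lymphopenia, individual components of cytokine release and transient interferon reactions are excepted in 12.6 and do not stop treatment. This reduces the pool of early events that move a patient.
- Inhibitor doses may be held or rescheduled (6.5.2), so instability at day 14 can delay receipt rather than prevent it.
- Patients stopped for toxicity are still followed for response (4.1). Some may respond, so early loss need not be all non-response.
- The suspension affects one subgroup's enrollment, pending review by people who would know whether the patient had a contraindication.

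A reader might infer that a toxicity comparison between inhibitor and no-inhibitor groups is biased. With 25% toxicity in both groups and half of it early, receipt grouping would give 1.5/10.5 = 14% against 2.5/5.5 = 45%. The plan contains no such comparison: toxicity is assessed in all patients together, and the remark about the 14-day delay can be read as attribution by timing. A reader might also take 1 − 0.875^12 = 0.80, the chance that a planned-inhibitor patient trips the rule, as the size of the problem. The 4 contraindicated patients alone already trip it with probability 0.68, so the net increase is 0.26 (0.94 − 0.68), or 0.15 with a 5% early rate.

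**Conclusion.** The concern holds in limited form. As written, the subset is selected on a post-baseline outcome, and the suspension trigger does not match the group its decision concerns. On assumed inputs (12 planned and 4 contraindicated patients, 25% toxicity in both), the trigger probability rises from 0.68 to 0.94 when half of toxicity precedes day 14, and to 0.83 when the pre-day-14 rate is 5%. If 10-30% of planned patients are lost early as non-responders, a true 25% subset response rate appears as 28-36%. The early-toxicity and early-loss shares are assumptions, so the direction of the mechanism is better supported than its size.

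It would be wrong to infer that the primary conclusions are compromised. The all-patient toxicity boundary and the rule of at least 3 responses in 16 do not depend on receipt. No decision rule is stated for the 12-patient subset, and for at least 3 of 12 the exact false-positive rate stays below 0.05 up to about 30% early loss. The main efficacy harm is an inflated subset estimate. Correcting the definitions is worthwhile, but the point does not undermine the design.

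**What to change.** In 13.1 and 13.3.2, define the subset at enrollment: patients without a baseline contraindication to PD-1/PD-L1 inhibition (5.3.1, 5.3.9, 6.5), whether or not a dose was given. Report results by actual receipt descriptively only.

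In the last paragraph of 13.2.2, make the trigger group the same as the group the decision concerns, namely patients enrolled with a baseline contraindication. The rule refers to a toxicity without a grade, while 13.2.1 defines a safety event more narrowly. The sponsor should reconcile the two. That threshold is a separate matter and should not change as a by-product of this edit.

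The cost is wording in three paragraphs, using facts already settled at screening. No dose, schedule or treatment rule changes. The downside is that the subset may include a few patients who never received the inhibitor, so it describes the planned regimen rather than the regimen as delivered.

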13.3 Primary Endpoint: Efficacy

13.3.1 Definition of response

Irradiated and non-irradiated lesions will be separately tracked but response determined in totality. As indicated, patients who will be evaluated for this endpoint will have at least one trackable lesion by response evaluation criteria in solid tumors (RECIST) 1.1. Response will be defined as best overall response by RECIST 1.1 of complete or partial response for patients with at least one measurable lesion.

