2.2 Rationale for inclusion of subcutaneous interferon gamma

2.2.1 Scientific basis

As our therapy utilizes a transgenic TCR, we are dependent on antigen presentation by the primary tumor through class I MHC. We and others have shown that approximately 80% of MCC tumors downregulate MHC-I presenting an obstacle to T cell efficacy, and this is further true of tumors that have escaped immunotherapy.^{27,62} In 5 patients previously treated in an earlier version of this clinical trial, the only patient with a meaningful clinical response was the single patient with robust baseline class I MHC expression. Furthermore, that patient had loss of class I MHC expression in a single resistant lesion. Despite the small number of patients, this suggests that downregulation of class I MHC may be a key mechanism of resistance to transgenic TCR T cell therapy. However, this class I downregulation is typically reversible with one of several interventions, which include radiation treatment, epigenetic modifiers, chemotherapy, and cytokine treatments.²⁷ Earlier versions of this trial included either single fraction radiation to a subset of lesions (n=3 patients) or chemotherapy treatment (n=2 patients) without clinical efficacy in patients without baseline class I MHC expression. This indicated a different strategy was necessary to efficiently upregulate class I MHC in tumors.

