5.2.10 Participants must be at least three weeks from last systemic MCC treatment

At least 3 weeks must have passed since any: immunotherapy (for example, T-cell infusions, immunomodulatory agents, interleukins, MCC vaccines, intravenous immunoglobulin, expanded polyclonal TIL or LAK therapy), NK therapy, small molecule or chemotherapy cancer treatment, other investigational agents **or other systemic agents that target MCC**. There is no washout period for radiation.

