5.3 Exclusion Criteria

5.3.1 Active autoimmune disease

Active autoimmune disease requiring immunosuppressive therapy is excluded *unless discussed with the PI*. Patients with a history of autoimmune disease that was a contra-indication to PD-1 axis blockade treatment will be eligible, but will not receive PD-1 axis blockade treatment on trial.

5.3.2 Prior solid organ transplant or allogeneic hematopoietic stem cell transplant.

Kidney transplant will be considered on a case-by-case basis requiring discussion with PI. If kidney transplant, patient must have dialysis access, dialysis plan, supportive nephrologist, **willingness to stop transplant immunosuppression, and express understanding that rejection is likely**. Dialysis or costs related to transplant kidney will not be supported by the study. Participants having had any other solid organ transplants will be excluded, as will those with a history of allogeneic stem cell transplant.

5.3.3 Corticosteroid therapy at a dose equivalent of > 10 mg prednisone per day.

5.3.4 Concurrent use of other investigational agents or MCC directed therapies.

5.3.5 Any Medical or psychological condition other than Merkel cell carcinoma that would significantly increase the risk of harm to a subject or interfere with the interpretation of trial endpoints.

5.3.6 Active uncontrolled infection.

HIV positive participants on HAART with a CD4 count > 500 cells/mm³ are considered controlled, as are individuals with a history of hepatitis C who have successfully completed antiviral therapy with an undetectable viral load, and those with hepatitis B who have hepatitis well controlled on medication.

5.3.7 Uncontrolled concurrent illness.

Participants may not have uncontrolled or concurrent illness including, but not limited to, symptomatic congestive heart failure, unstable angina pectoris, cardiac arrhythmia, or psychiatric illness/social situations that would limit compliance with study requirements.

5.3.8 Untreated brain metastases.

Participants with small asymptomatic brain metastases (< 1 cm) or those with brain metastases previously treated with surgery or radiotherapy will be considered for inclusion at discretion of principal investigator, so long as other eligibility criteria are met.

5.3.9 Active treatment for prior immune related adverse event to any immunotherapy.

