6.4.3 Acute infusion reactions

Acute infusion reactions may occur with administration of FH-MCVA2TCR. Guidelines for the monitoring and treatment of acute infusion reactions are provided in **Sections 7.3 and 7.4**.

6.4.4 Guidelines for the determination of 1 or 2 cycles of T cell therapy

Each “cycle” of T cell therapy consists of one cycle of interferon gamma plus T cell infusion. Interferon gamma will be given with second infusions unless patient has had a grade 3 or higher toxicity attributed to interferon gamma.

Twelve weeks after first T cell infusion, restaging and evaluation of peripheral blood persistence of infused transgenic T cells will be performed, and patients will be considered for a second cycle (second class I MHC upregulation procedure plus second infusion of transgenic T cells). A second cycle may be given between 6 and 12 weeks after the first cycle in patients who have progressive disease and <5% TCR T cells among CD8 T cells in the blood. Avelumab or pembrolizumab infusions will continue up to the second infusion. Decision-making surrounding a second cycle will be at the discretion of the investigator and will be generally made following the below guidelines:

Individuals with progressive disease and non-persisting T cells (<5% of CD8) may be considered for a second infusion if they meet eligibility criteria for treatment as described in **Section 5** above. Patients with symptomatic progression may receive debulking radiotherapy or chemotherapy for one or more cycles per standard of care between the first and second T cell infusions, but the interval between the end of chemotherapy and the second infusion must be at least 3 weeks. Treatment with avelumab or pembrolizumab will be discontinued during chemotherapy and will be resumed 1 week before the second infusion of T cells.

Individuals with **progressive disease** and persistent T cells (>5% of CD8) will no longer receive additional T cells or avelumab or pembrolizumab on study. They will leave the treatment phase of the study and will transition to long-term follow-up.

Individuals with **complete response** will remain on the treatment phase of the study and will continue to receive avelumab or pembrolizumab to complete a year of treatment. However, they will not receive

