11.3 Pre-Treatment Evaluations

Results of tests and procedures conducted as per standard of care purposes prior to screening may be used for research purposes if conducted within the protocol-defined window.

The screening consent and HIPAA authorization must be signed before any non-standard of care evaluations are performed.

Baseline evaluations include:

1. Medical history and physical examination including prior therapies and response to therapy if known, and Karnofsky performance status.
2. Laboratory tests, including:
 - a. CBC, differential, platelet count
 - b. Comprehensive metabolic panel
 - c. LDH
 - d. Fred Hutch (PSBC) Donor Battery Panel (should be performed within 30 days of leukapheresis)
 - e. Serum ferritin
 - f. Serum CRP
 - g. Uric acid

- h. Serum IL-6
- i. Prothrombin time (PT), partial thromboplastin time (PTT) (should be performed within 30 days of leukapheresis)
- j. Serum pregnancy test for females of childbearing potential within 14 days of planned leukapheresis.
3. Confirmation of diagnosis by internal pathology review of initial or subsequent biopsy or other pathologic material at Fred Hutch.
4. Baseline pulse oximetry and documentation of O₂ saturation on room air
5. Baseline 12-lead EKG
6. Patients age 60 years or older: Echocardiogram or MUGA scan
7. Baseline imaging (generally CT chest/abdomen/pelvis (and if present affected extremity), MRI brain if history of brain metastasis or neurologic symptoms, CT neck if prior cervical adenopathy, MRI or PET may be substituted as clinical judgement dictates). Imaging must be obtained within 45 days of prior to start of first planned FH-MCVA2TCR infusion
8. For skin/cutaneous tumors, representative/target tumors should be photographed pre treatment for baseline measurements (optional).
9. Clinical documentation of relapsed disease (imaging and/or biopsy).

Research samples:

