11.6 Response Assessment

Participants will have evaluation of tumor burden at baseline (physical exam with tumor measurements, cross-sectional imaging as detailed above, RECIST and imRECIST reads of cross-sectional imaging), at 4 and 12 weeks after first T cell infusion, at 4 and 12 weeks after second infusion (if given), and then at discretion of treating oncologist (suggested frequency every 3-6 months). Patients with progressive disease on 4 week imaging but clinical stability may remain on study given the possibility of delayed clinical responses to immunotherapy. Imaging should also be performed if suspicion of progression. Imaging will be performed on a clinical basis with RECIST/imRECIST reads on a research basis. For skin/cutaneous tumors, representative/target tumors should (optionally) be photographed at key response assessment/measurement time points (day 14, 12 weeks, months 3, 6, 9, and 12 post infusion). Patients without measurable lesions will not be evaluable for response, but will be evaluable for safety endpoints.

Participants will have clinical pathology evaluation of tumor at baseline, at approximately 12 weeks after first T cell infusion, and if clinically suspected to have progression. Additional research biopsies are planned prior to T cell infusion, at 2 weeks post T cell infusion and at 12 weeks after second T cell infusion, and additional research tissue may be requested from clinical biopsies.

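### The primary response pools irradiated with non-irradiated lesions and has no stated cut-off at other anti-tumor therapy, so shrinkage from that therapy could be credited to the regimen

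*Combined protocol and SAP*

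**What the plan says.** The primary efficacy endpoint is best overall response of complete or partial response by RECIST 1.1 (protocol 13.3.1). The same section says of lesions: "Irradiated and non-irradiated lesions will be separately tracked but response determined in totality". Three or more responders among 16 lead to the conclusion that the regimen is potentially efficacious, against a fixed 5% benchmark (3.1.2 and 13.3.2).

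Other sections determine whether other therapy can reach this endpoint:

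- **Entry.** Section 5.2.10 states: "There is no washout period for radiation". Section 11.3 states: "Imaging must be obtained within 45 days of prior to start of first planned FH-MCVA2TCR infusion".
- **Between infusions.** Section 6.4.4 states: "Patients with symptomatic progression may receive debulking radiotherapy or chemotherapy for one or more cycles". Section 6.4 also lets the second infusion be delayed for bridging chemotherapy. Section 11.6 re-images at weeks 4 and 12 after a second infusion.
- **After a toxicity stop.** Section 13.2.2 keeps following these patients for response.
- **Cut-offs.** Section 12.5 ends detailed adverse event collection when new anti-tumor therapy begins. No matching sentence exists for response.
- **Exclusion.** Section 5.3.4 excludes "Concurrent use of other investigational agents or MCC directed therapies".

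Response by immune RECIST is a separate secondary objective (3.2.5).

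**The concern.** The endpoint is meant to measure what the T cell regimen does. As written, the rule measures every lesion from baseline onward, whatever else has treated it. Radiation was part of earlier versions of the regimen (2.2.1) and the sentence in 13.3.1 may date from then, but it is in force, and irradiated lesions can still occur.

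The decision turns on three patients, so a single response caused by other therapy could change the conclusion. Two analysts could also classify the same patient differently, because nothing in 13.3.1 settles the case. Such a rule should be fixed before outcomes are known.

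**Working it through.** **Routes in the text, strongest first**

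1. *Radiation between baseline scan and infusion.* There is no washout, and the scan may precede infusion by up to 45 days. Shrinkage would then be measured against a pre-radiation baseline. Radiation before the scan is largely absorbed into the baseline measurement, apart from a delayed effect.
2. *Radiotherapy or chemotherapy between infusions.* Section 6.4.4 allows it for symptomatic progression, with imaging afterwards. This route is limited if best response is taken as fixed at progression. The protocol does not say so, and under 11.7 progression ends active treatment only after the second infusion.
3. *Other therapy after a toxicity stop.* Response follow-up continues under 13.2.2 with no stated end at new therapy.

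**Reproducing the plan's figures**

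Inputs from 13.3.2: n = 16, rule of 3 or more, benchmark 5%, alternative 25%, one-sided .05.

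- Type I error: P(Bin(16, 0.05) ≥ 3) = 1 − (0.4401 + 0.3706 + 0.1463) = 0.043. This matches the stated .04.
- Exact power: P(Bin(16, 0.25) ≥ 3) = 0.803. The stated 84% matches a one-sided normal approximation (0.846), so the exact figure is used below.

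**Effect of other therapy on the chance of passing**

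The documents give neither the number of exposed patients, k, nor the chance q that other therapy alone produces a response. Both are assumptions. With background rate b:

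- X ~ Bin(k, 1 − (1−b)(1−q)) for exposed patients
- Y ~ Bin(16−k, b) for the rest
- chance of passing = P(X + Y ≥ 3)

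For k = 1, q = 5%, b = 5%, the exposed patient responds with probability 1 − 0.95 × 0.95 = 0.0975. The chance of passing is 0.0975 × P(Bin(15, 0.05) ≥ 2) + 0.9025 × P(Bin(15, 0.05) ≥ 3) = 0.0975 × 0.1710 + 0.9025 × 0.0362 = 0.049.

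| k | q | b = 5% | b = 2% | b = 1% |
|---|---|---|---|---|
| 0 | – | 0.043 | 0.004 | 0.001 |
| 1 | 5% | 0.049 | 0.005 | 0.001 |
| 4 | 10% | 0.107 | 0.028 | 0.013 |
| 1 | 20% | 0.069 | 0.010 | 0.002 |
| 4 | 20% | 0.194 | 0.081 | 0.052 |
| 4 | 30% | 0.300 | 0.164 | 0.123 |

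The lower backgrounds are shown because 3.1.2 puts spontaneous regression at up to 1% and calls 5% conservative.

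**Cost of a cut-off**

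If a fraction f of true responses arises only after other therapy, those responses leave the primary count and power is P(Bin(16, 0.25(1−f)) ≥ 3). The fractions are assumed.

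| f | response rate counted | power |
|---|---|---|
| 0 | 0.25 | 0.80 |
| 5% | 0.2375 | 0.77 |
| 10% | 0.225 | 0.73 |
| 20% | 0.20 | 0.65 |

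**The case against.** The case on the other side has substance.

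- **RECIST 1.1 may already settle some of this.** Its rules are not in the documents, so nothing can be claimed about them either way. What stands is that the protocol text itself gives no cut-off and does state the pooling rule.
- **Bridged patients have already progressed.** The separate immune RECIST objective suggests that later responses may belong there. This weakens the second route, but 13.3.1 does not say it, and it does not touch radiation between scan and infusion.
- **Pooling also protects.** One irradiated lesion cannot carry a response while others grow. The exposure is therefore mainly in patients with few measurable lesions.
- **The entry route is narrow.** Section 5.3.4 excludes concurrent MCC-directed therapy and 11.3 asks for documented relapsed disease. Neither clearly forbids radiation after the scan. How often it would happen is unknown.
- **Earlier experience points to a small effect.** Earlier versions gave radiation to a "subset of lesions (n=3 patients) or chemotherapy treatment (n=2 patients) without clinical efficacy in patients without baseline class I MHC expression". Of those five patients, "the only patient with a meaningful clinical response was the single patient with robust baseline class I MHC expression". But 0 responses in the other 4 has a one-sided 95% upper limit of 1 − 0.05^(1/4) = 0.53. It also sets the responder aside after the fact, and single-fraction radiation to a subset of lesions is not debulking radiotherapy.

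A reader might infer that the false-positive rate is really about 0.17. That figure is P(Bin(15, 0.05) ≥ 2) = 0.171, the chance of passing given that one response due only to other therapy has already occurred. It is conditional, not the design's error rate. At 2% and 1% backgrounds it is 0.035 and 0.010. It may also double count, since 13.3.2 describes responses to alternative therapies as rare when setting the 5%, so part of the 5% may already allow for them.

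**Conclusion.** The point holds in a limited form. The stated rule, followed as written, can credit shrinkage from other anti-tumor therapy to the regimen. The route through radiation between baseline scan and infusion is clear, the bridging route is weaker, and the route after a toxicity stop is open on the text.

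The size is not established. With 1 to 4 exposed patients and q of 5-10%, the chance of passing is 0.049-0.107 at a 5% background and 0.001-0.028 at 1-2%, the latter below the stated .04. Material inflation at the lower backgrounds needs larger assumptions, such as four exposed patients with q of 20%. A reader might conclude that the 3-of-16 rule is invalid or that the trial is likely to pass falsely. The documents do not support that, because they give neither k nor q.

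The gap is worth closing because so few responders decide the result and the remedy is cheap.

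**What to change.** Add one paragraph to 13.3.1:

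(a) The primary best overall response uses assessments from the first T cell infusion up to the first anti-tumor therapy other than the T cells, interferon gamma and avelumab or pembrolizumab. Say expressly that this includes radiotherapy or chemotherapy given between infusions under 6.4.4, since a phrase such as non-protocol therapy could be read to miss it. A response reached before that point stands. Patients not in response by then remain in the denominator as non-responders.

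(b) Shrinkage of a lesion irradiated between the baseline scan and infusion does not count towards the primary response. The separate tracking already planned is enough to apply this. A patient with no other measurable lesion remains in the denominator as a non-responder, so the 3-of-16 rule is unchanged.

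(c) The pooled response over all lesions, and responses after other therapy, are reported as sensitivity or secondary analyses from scans already scheduled.

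Under this rule, if the 5% benchmark applies to the responses counted, the exact type I error stays at 0.043.

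**Cost.** One paragraph and the start date of each other therapy; 12.5 already requires the date of new anti-tumor therapy. No scans are added. True responses that arise only after other therapy leave the primary count, with the loss of power tabulated above.

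No change to permitted therapy is proposed. Sections 5.3.4 and 6.4.4 should be reconciled on therapy between infusions.
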